1.0 Study Design and Methods

Study Design

To address the study objectives, a pilot randomized controlled trial will be conducted.

Study population:

Group 1: Veterans

A convenience sample of Veterans , who are screened and diagnosed with Parkinson's disease (PD) and mild cognitive impairment in the executive function domain will be enrolled. Targeted enrollment for the intervention is 45; they will be randomized to one of three groups: CCT+PRIIS (n=15), CCT+PRIIS control (n=15) or CCT control +PRIIS control (n=15).

Group 2: Knowledgeable Informants

We will also enroll knowledgeable informants/caregivers of the enrolled Veterans. Thus, we will be enrolling civilians (however it is possible that caregiver could be a Veteran and this is acceptable). The purpose for enrolling a caregiver is to obtain their perspective on functional changes related to cognitive impairment in the Veteran living with PD. To obtain their perspective, they will complete the PD-Cognitive Functional Rating Scale (PD-CFRS) at three different time points during the study. The planned activities for the caregiver are the following: consent, demographic form, PD-CFRS at three different time points. The consent form, demographic form and PD-CFRS will be completed at their first visit. We will mail them the form when their Veteran completes the RCT, we will mail them the form again one month later. A knowledgeable informant/caregiver is not required in order for the Veterans to enroll. Targeted enrollment is 45, however we anticipate having to enroll 60 civilians due to Veterans being withdrawn – and thus the associated civilian will need to be withdrawn.

Below we list the inclusion and exclusion criteria for both Veterans and Knowledgeable Informants.

Group 1: Veterans

In general, eligibility criteria target Veterans with idiopathic PD and not other forms of parkinsonism. Thus, only Veterans older than 50 with PD diagnosed according to UK Parkinson's Disease Society Brain Bank

Diagnostic Criteria will be eligible. PD medication can influence cognitive function, thus, only participants receiving stable medication (i.e., no changes in medication or dose for the past month) and who are expected to remain on stable medication for the duration of the RCT will be eligible.

Inclusion criteria for Veterans:

- Diagnosis of PD as determined by the UK Parkinson's Disease Society Brain Bank Diagnostic Criteria⁴⁶
- age 50 and older

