Repeated measures/study outcomes are included in a standardized battery of test that will be repeated at baseline, endpoint and follow-up. The battery is expected to take approximately 130 minutes to complete.

Tests administered during screening (e.g., the BDI-II, MoCA, BAI, and HVLT, Memory for Intentions Test, and Modified Fatigue Impact Scale) will not be replicated at baseline, but are included in Table 3 below to indicate it is a repeated measure.

Table 3: Repeated Measures Assessment Tools used in the RCT			
Assessment Name (Abbreviation)	Outcome	Construct measure	Time to complete (min)
NIH-EXAMINER components:	1° (composite score of 7 tests listed below)	Executive function	29 total
Dot counting	2°	Working Memory	7
1-back			5
2-back			5
Flanker	2°	Cognitive Control	5
Set Shifting			5
Letter	2°	Verbal Fluency	1
Category			1
Hopkins Verbal Learning Test-Revised (HVLT)	2°	Memory	10
Symbol Digit Modalities Test (SDMT)	2°	Processing speed	5
The Memory for Intentions Test (MIST)	2°	Prospective memory	15
Monetary-Choice Questionnaire	2°	impulsivity	10
Parkinson's Disease-Cognitive Functional Rating Scale (PD-CFRS)	2°	Real-life function	5
The Activity Measure for Post-Acute Care™ (AM-PAC™) –Applied Cognition questionnaire	2°	Real-life function	10
Timed instrumental activities of daily living (iADL)	2°	Real-life function	15
Beck Depression Inventory-II	2°	Depression	10
Beck Anxiety Inventory	2°	Anxiety	10
Starkstein Apathy Scale	2°	Apathy	5
Montreal Cognitive Assessment	2°	Global Cognition	10
Epworth Sleepiness Scale	2°	Sleepiness	5
Modified Fatigue Impact Scale	2°	Fatigue	5
			Total Time: 144 minutes

Phase 4: Intervention

Participants will be randomized to one of three groups: CCT+PRIIS (n=15), CCT+PRIIS control (n=15) or CCT control +PRIIS control (n=15) and issued a VA iPad to take home and complete the study intervention.

Participants and researchers who are administering and scoring outcome measures will be blinded to group assignment. Effectiveness of blinding will be evaluated by using data collected from mid-point and endpoint questionnaires that assess perception of training intervention⁶⁹. The PI will oversee the RCT and coordinate research procedures and thus will not be blinded to treatment assignments. [name], who will be blinded to group assignments, will coordinate sensitive aspects of the study that require blinding.

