MCID for the NIH-EXAMINER executive composite score will be computed using two anchor-based MCID approaches. First, a within patient score change approach will be used, which defines MCID as the mean change between the outcome scores (NIH EXAMINER Executive composite score) of a group of patients selected per their answers. Second, a sensitivity- and specificity-based approach will be used. This anchor-based approach is useful to calculate the threshold that allows for the best discrimination between groups of patients. The outcome score that produces the greatest and most balanced sensitivity and specificity for discriminating patients with minimal change from patients without any change will be considered as the MCID. Used in conjunction with MCID estimations, sensitivity is the proportion of the patients having change on the external criterion (PD-CFRS) and whose outcome score (NIH EXAMINER Executive composite score) change exceeds the threshold MCID value. Similarly, specificity is the proportion of subjects without any changes on the external criterion (PD-CFRS) and whose outcome changes are below the threshold MCID value. Full, partial and non-responders will be defined using the MCID in both the sham and active rTMS groups (i.e., full = > 1 MCID, partial= 1 MCID, non= < 1 MCID).

The psychometric properties of the PD-CFRS (both self-report and informant report assessed separately) will be assessed using the Rasch model (i.e., construct validity) and concurrent validity will be examined using traditional correlational methods (i.e., concurrent validity with NIH-EXAMINER). For the PD-CFRS, the interrater agreement between self- and informant ratings will be calculated using the Corrected Discrepancy score, which is a rigorous measure correcting for between-subject differences in actual level of scoring.

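### The EXAMINER MCID comes from at most 45 Veterans and one anchor that is itself under test; without an interval or internal validation it will be imprecise and its sensitivity and specificity optimistic

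*Combined protocol and SAP*

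**What the plan says.** Section 1.0 states that "a pilot randomized controlled trial will be conducted" and that "Targeted enrollment for the intervention is 45", split equally over three arms. In Section 5.0 the EXAMINER composite, which Table 3 marks as the primary outcome, is to receive an MCID in two ways. One is the mean change in patients picked by their anchor answers. The other is a cut-off search that selects "The outcome score that produces the greatest and most balanced sensitivity and specificity for discriminating patients with minimal change from patients without any change". PD-CFRS is the external criterion in both definitions of accuracy. The section then says "Full, partial and non-responders will be defined using the MCID", and applies this to sham and active rTMS groups, which are not arms of this trial.

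The next paragraph puts PD-CFRS itself under examination, by a Rasch model and because "concurrent validity will be examined using traditional correlational methods (i.e., concurrent validity with NIH-EXAMINER".

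The plan does not define minimal change on PD-CFRS. It does not say whether the self-report or the informant version is the anchor, although "A knowledgeable informant/caregiver is not required in order for the Veterans to enroll", so the informant version may be available for fewer people. It does not say which of the two MCIDs defines responders. It mentions no confidence interval, resampling, validation sample or outside MCID. Table 3 also lists the AM-PAC "Applied Cognition questionnaire" as a measure of real-life function at the same visits.

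**The concern.** An anchor-based MCID is only as good as the link between anchor and outcome. Here that link is one of the things the study sets out to examine, and the plan does not ask for it to be reported beside the MCID. A cut-off chosen because it separates two groups well in a given sample will look better in that sample than elsewhere, and with few people in each group the cut-off itself moves a great deal from sample to sample.

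At stake are the responder classification, which takes the MCID as a known constant, and the sensitivity and specificity reported with it. Section 3.0 says the pilot data will support a proposal for a larger study, so a reader of that proposal needs to see how uncertain the value is.

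**Working it through.** **Inputs from the plan.** Three arms of 15 give 3 x 15 = 45 Veterans, which matches the stated target. The plan gives no MCID precision, responder rate, SD of change or anchor correlation, so there is no further figure to reproduce.

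**Assumed inputs.** Changes in anchor and EXAMINER are bivariate normal with SD 1 and mean 0.3, and correlation r of 0.3, 0.5 or 0.7. Minimal change is 0.5 to 1.2 SD on the anchor; no change is within 0.5 SD of zero. Results are in SD of EXAMINER change.

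**Step 1: how many people inform the MCID.** In standard units, minimal change is 0.2 to 0.9 and no change is -0.8 to 0.2.
- Minimal change: 0.816 - 0.579 = 0.237, and 45 x 0.237 = 10.6 people.
- No change: 0.579 - 0.212 = 0.367, and 45 x 0.367 = 16.5 people.

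The other 18 or so are in neither group.

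**Step 2: mean-change MCID.** The minimal-change group has mean standardised anchor change (0.391 - 0.266)/0.237 = 0.53. Its expected EXAMINER change is 0.3 + 0.53r, or 0.46 at r = 0.3. The SD within the group is about 0.96, so the standard error is 0.96/√10.6 = 0.29 and the 95% range about 0.46 ± 1.96 x 0.29, or -0.1 to 1.0. Simulation, which lets the group size vary, gives the last column below.

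**Step 3: cut-off MCID.** The plan's wording asks for both high and balanced accuracy. Two readings were simulated (n = 45, 4,000 runs): the cut-off nearest sensitivity = specificity = 1, and the cut-off where the two are closest to equal.

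| r | Nearest to perfect: 95% range (negative) | Most balanced: 95% range (negative) | Mean change: 95% range |
|---|---|---|---|
| 0.3 | -0.4 to 1.2 (about 16%) | -0.1 to 0.8 (7 to 8%) | -0.15 to 1.07 |
| 0.5 | -0.3 to 1.1 (about 12%) | -0.1 to 0.8 (about 5%) | 0.02 to 1.09 |
| 0.7 | -0.1 to 1.0 | 0.04 to 0.77 | 0.22 to 1.12 |

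The percentages move by a point or two between runs.

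**Step 4: optimism.** The measure is sensitivity + specificity - 1.
- The no-change group has mean standardised anchor change (0.290 - 0.391)/0.367 = -0.28, so the groups differ on EXAMINER by r x (0.53 + 0.28) = 0.81r.
- At r = 0.3 that is 0.24 SD. Divided by a within-group SD of 0.96 it is 0.25, and the best true value any cut-off can reach is about 2Φ(0.25/2) - 1 = 0.10.
- In simulation with the nearest-to-perfect rule, apparent against true values were 0.26 v 0.09 at r = 0.3 (excess 0.17) and 0.43 v 0.28 at r = 0.7 (excess 0.15). The excess was similar at r = 0.5.
- This optimism comes from maximising. A rule that only equalised sensitivity and specificity showed almost none in the same set-up.

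**Step 5: different assumptions.** With mean change 0 and the anchor split so that 30% improve, the nearest-to-perfect cut-off ranged from -0.43 to 0.89 at r = 0.3 and -0.16 to 0.84 at r = 0.7. Apparent against true accuracy was 0.32 v 0.19 and 0.60 v 0.48. At r = 0.3 the share of people at or above the cut-off ran from 22% to 64% through sampling alone.

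**Step 6: comparison between arms.** With one cut-off pooled over arms, 15 v 15, r = 0.3 and 40% improved, Fisher's exact test rejected in 1.7% of null runs. Power for a true difference of 0.8 SD was 22% on responders against 56% on the continuous score.

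**The case against.** The best defence is that this is a secondary product of a pilot. Responder status is not an outcome in Table 3, and the mixed model for the primary outcome does not use the MCID. That stands, and it limits the weight of the point. It does not justify a point value without an interval, since showing uncertainty is part of a pilot's job.

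Several stronger readings are tempting and are not supported.

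- A reader might infer that the responder result is noise. That depends on the anchor correlation and on how many people show minimal change, and the documents give neither. At r = 0.7 the mean-change MCID and the most balanced cut-off both exclude zero.
- A reader who takes the rule as simply maximising sensitivity plus specificity would get about -1.15 to 1.81 SD at r = 0.3, negative in 33% of runs. The plan also asks for balance, which rules that reading out and narrows the range.
- A reader might infer that deriving and applying the cut-off in the same people inflates false positives between arms. It does not (step 6); the cost there is power.
- That the same people are classified is itself an inference, because the sentence names rTMS groups. It is a reasonable one, since no other sample is described.
- Nothing says the MCID will be carried into a larger trial as established.

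A hard threshold on the correlation is also open to objection. At n = 45 an observed r of 0.3 has a 95% interval of tanh(0.310 ± 1.96/√42), about 0.01 to 0.55, so such a rule would turn largely on chance. Reporting responders only when the interval excludes zero would make reporting depend on the result.

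**Conclusion.** The point holds in a limited form and is worth acting on. Followed as written, the plan yields an MCID whose 95% sampling range at n = 45 is roughly 0.7 to 1.6 SD wide across the rules and correlations in step 3, and which can fall below zero at r of 0.3 by any of the methods. To the extent that the cut-off is chosen to maximise accuracy, the reported sensitivity and specificity are too high, by about 0.15 on their sum under the nearest-to-perfect rule. The exact sizes rest on assumed normal changes, correlations and group definitions, and loss of participants would widen the ranges. The direction did not change under the alternative assumptions. The supportable statement is that the MCID is imprecise and its accuracy overstated; the primary analysis is untouched.

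**What to change.** In Section 5.0:

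1. State in advance which PD-CFRS version, self or informant, is the anchor, and what score change counts as minimal change and as no change.
2. Report the correlation of change in EXAMINER with change in PD-CFRS beside the MCID, without using it as a gate.
3. Give both MCIDs with bootstrap 95% confidence intervals that repeat the cut-off search in each resample, and report optimism-corrected sensitivity and specificity.
4. Repeat the derivation with AM-PAC Applied Cognition as a second anchor.
5. Show responder proportions at the MCID estimate and at both interval limits, labelled exploratory.
6. Replace the reference to rTMS groups with the three arms of this trial.

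The cost is a little more analysis on data already collected, with no added visits or participants. The downside is that the MCID may be shown to be too imprecise to use.

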5.0 Data Analysis

All test administrators will undergo the same training. Data will be cleaned and tested for normality (if normality tests fail, appropriate transformations will be made), and proper missing data imputation techniques will be used. Test for multicollinearity will be made. The 3 treatment groups will be characterized using descriptive statistics for demographic factors, disease-related variables, and medication use. Groups will be examined for comparability according to the descriptive variables using ANCOVA and mixed-effects model with random subject effects. For ANCOVA, type I error rate ($\alpha=0.05$) will be adjusted for multiple comparisons using Bonferroni corrections.

Neuropsychological Data Analytical Approaches. For Aims 2 and 3, data will be analyzed using a two-level longitudinal mixed effects model with random subject effects to incorporate correlation of measurements nested within the same subject. Covariates will include medication dose, anxiety, apathy, and depression level. Parameters will be estimated using measurements from baseline, endpoint, and follow-up. The group by time interaction parameter will be used to examine the difference of the trends between the three groups. Significance of this parameter will indicate that treatment is efficacious in terms of EF over time when adjusted by covariates. To assess immediate effects of CCT, an experiment group contrast will be formed using test score means at baseline and endpoint and a control group contrast will be made with those same types of means. To assess sustainability of CCT effects, contrasts using means of test scores at endpoint and follow-up will be made for each group. Estimates of variance components from mixed-model analysis will be used to calculate test statistics. Data analysis will be performed using SAS 9.3 Proc Mixed. This modeling process will be reported for each outcome of interest in Aims 2 and 3. Potential moderators of the effects of the CCT will be explored through Pearson correlations and regression analyses. Factors include, age, age at PD onset, disease duration, MoCA score, depression, anxiety, apathy, L-dopa equivalent dose, PD-MCI subtype diagnosis,

scores on training perception, prior computer use and cognitive training. Co-morbidities and medications will be considered as confounders.

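### The responder rule for the primary composite names sham and active rTMS groups that this three-arm training trial does not have, and its partial level is a single value likely to hold very few Veterans

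*Combined protocol and SAP*

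**What the plan says.** Section 1.0 (Study population, and again under Phase 4: Intervention) randomises 45 Veterans to CCT+PRIIS, CCT+PRIIS control, or CCT control+PRIIS control, 15 in each. Table 3 marks the NIH-EXAMINER composite of seven tests as the primary outcome.

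Section 5.0 is first written for that design: "The 3 treatment groups will be characterized using descriptive statistics", and the group-by-time term of the mixed model compares three groups.

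The MCID paragraph that follows computes two anchor-based values for the composite. The first is a within-patient approach, "which defines MCID as the mean change between the outcome scores" in a selected group. The second is a cut-point: "The outcome score that produces the greatest and most balanced sensitivity and specificity", judged on how well it tells minimally changed patients from unchanged ones, is taken as the MCID. The responder rule comes last: "Full, partial and non-responders will be defined using the MCID in both the sham and active rTMS groups", with levels "full = > 1 MCID, partial= 1 MCID, non= < 1 MCID".

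**The concern.** The rule refers to a different design. It names two groups, one sham and one active, of a treatment that is not given in this trial. Deleting the word rTMS would not repair it, because the sentence still assumes two groups where there are three, and the arm with active CCT and control PRIIS is neither wholly active nor wholly control.

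The middle level is defined by equality. On a seven-test composite few people will change by exactly the MCID, so a three-level scale may in practice be a two-level one.

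Two further choices are open. The rule refers to the MCID after two have been computed, and it names no visit although there are assessments at endpoint and one month later. If arms, visit and threshold are settled only when the data are in hand, the responder proportions depend on choices that a written plan should fix beforehand.

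**Working it through.** **Groups.** The stated enrolment reproduces: 3 × 15 = 45.

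| Place | Groups |
|---|---|
| 1.0, Study population and Phase 4 | 3 training arms of 15 |
| 5.0, descriptive statistics and mixed model | 3 |
| 5.0, responder rule | 2 (sham rTMS, active rTMS) |

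rTMS and sham appear nowhere else in the available text. Section 5.0 also mentions an experiment and a control contrast for the immediate effect of CCT, but does not say which arms enter each.

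**Partial level.** The documents give no MCID value, no SD of change and no score step, so these are assumptions: change is Normal, *r* is the score step in SD of change, and *d* is the distance of the MCID from the mean change in SD. For an MCID that lies on a possible score:

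P(change = MCID) = Φ(d + r/2) − Φ(d − r/2); expected number = 45 × P.

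Example: r = 0.2, d = 0.5 gives P = 0.0703, and 45 × 0.0703 = 3.2.

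The table sets this beside simulated means (n = 45, 4,000 runs per step, mean change 0.3 SD, correlation with the anchor 0.4). The mean-change MCID was rounded to the nearest score step. The cut-point MCID was placed on an observed score.

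| r | 45 × P, d from 0 to 1 | Simulated, mean-change MCID | Simulated, cut-point MCID |
|---|---|---|---|
| 0 (continuous) | 0 | 0 | 1.0 |
| 0.01 | 0.11–0.18 | 0.16 | 1.1 |
| 0.05 | 0.5–0.9 | 0.8 | 1.5 |
| 0.1 | 1.1–1.8 | 1.7 | 2.1 |
| 0.2 | 2.2–3.6 | 3.3 | 3.4 |

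A cut-point on an observed score puts at least one Veteran at the threshold by construction. A cut-point midway between adjacent scores gives 0 at every step, and so in general does a mean-change MCID that is not rounded.

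A less favourable count takes one Veteran as sitting at the threshold and adds the other 44: 1 + 44 × P. At r = 0.2 and d = 0 this is 1 + 44 × 0.0797 = 4.5. At r = 0.25 it gives 4.2 to 5.4 for MCIDs of 0.2 to 0.8 SD and mean changes of 0 to 0.5 SD. A separate simulation at r = 0.25, over anchor correlations of 0.3 to 0.7 and 30% or 50% changed on the anchor, gives 4.1 to 4.4.

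**Ties.** Sensitivity counts a patient whose "change exceeds the threshold MCID value"; specificity counts those "whose outcome changes are below the threshold MCID value". A change equal to the threshold is counted in neither, yet equality is what defines the partial level.

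**The case against.** The strongest reply is that the rule works patient by patient. It compares one change with one threshold, and no arm label enters. The plan specifies no two-group responder table and attaches no test, so an analyst could tabulate all three arms. That stands, and it rules out two stronger readings. A reader might infer that the 15 Veterans in the CCT+PRIIS control arm cannot be classified; they can. A reader might also infer that the results must be split 15 v 30, 30 v 15, or 15 v 15 with one arm left out; the documents call for no such table. Strictly, no arm is an rTMS arm, so the middle arm is singled out only after the other two have been mapped by analogy.

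It can also be said that the stated purpose of the experiment and control contrasts, the effect of CCT, leans towards counting both CCT arms as experimental. It does lean that way, but the text does not say so, and that sentence concerns the mixed model rather than the responder rule.

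On the partial level, the counts rest on assumed steps, and a coarse score gives 4 or 5 Veterans. A flat statement that the level will be empty is therefore not supported. What stands without any simulation is that a class defined by one exact value is a poor middle category.

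On the choice of MCID, the text favours the cut-point value, since it says that this one will be considered the MCID. The responder rule itself does not say which of the two it uses.

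**Conclusion.** The rule is wrong as written. The grouping it names does not exist in this trial, and its middle level is a single value. The first point rests on the text alone. The size of the second depends on the score step: on average 0 to about 3 of 45 for steps up to 0.2 SD of change (4.5 on the least favourable count at 0.2 SD), and about 4 to 5 at 0.25 SD, under Normal change and the MCID positions shown.

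Because the rule concerns the primary outcome, a reader might infer that the primary analysis is compromised. It is not. The mixed model is written for three groups, and randomisation, sample size and data collection are unaffected. The consequence is limited to a descriptive responder classification in a pilot. The wording should be corrected before data are seen.

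**What to change.** Replace the rTMS sentence with wording such as: Responders (change from baseline to endpoint of at least 1 MCID) and non-responders (less than 1 MCID) will be tabulated in each of the three randomised arms (CCT+PRIIS, CCT+PRIIS control, CCT control+PRIIS control); change from baseline to follow-up will be reported separately.

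In the same place, state which of the two MCIDs sets the threshold and show the classification under the other alongside. If a partial level is wanted, keep three levels but give it a range, fixed before data are seen, in place of equality. A change equal to the MCID should be assigned the same way in the sensitivity and specificity definitions and in the responder rule; this is a small clarification.

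The cost is SAP wording only. The one loss is the three-level label, unless a range for the partial level is set in advance.
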